- f) Absolute neutrophil count $< 1500 \times 10^6/L$
- g) Hb level < 100 g/L
- h) Platelets $< 100 \times 10^9/L$
- i) Creatinine clearance < 60 ml/min as calculated by the Schwartz formula:
 - i) $CrCl (ml/min/1.73m^2) = [length (cm) \times k] / Serum Cr$
k = 0.55 for children 3 to < 13 years; k = 0.55 for adolescent females 13 to < 18 years of age; k = 0.7 for adolescent males 13 to < 18 years of age

4) Allergies and Adverse Drug Reaction

- a) History of hypersensitivity to drugs with a similar biochemical structure to DCV or SOF
- b) Any other criteria or known contraindication that would exclude the participant from receiving DCV or SOF (see section 4.3 of DCV and SOF SmPCs)

5) Other Exclusion Criteria

- a) Prisoners or participants who are involuntarily incarcerated. (Note: under specific circumstances a person who has been imprisoned may be included as a participant. Strict conditions apply and Bristol-Myers Squibb approval is required).
- b) Participants who are compulsorily detained for treatment of either a psychiatric or physical (eg, infectious disease) illness
- c) Concurrent enrolment in another interventional clinical study

Eligibility criteria for this study have been carefully considered to ensure the safety of the study participants and that the results of the study can be used. It is imperative that participants fully meet all eligibility criteria.

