6.3.2.4 Laboratory Tests at Baseline

Laboratory test abnormalities at baseline are summarized as categorical parameters using toxicity grades separately for SI and US units. Percentages are based on participants with measurements.

Commonly collected laboratory tests that are graded using the Division of AIDS (DAIDS) Table for Grading the Severity of Adult and Pediatric Adverse Events (2004)⁴ toxicity grades (Grades 0, 1, 2, 3, 4; Grade 1 to 4; Grade 3 to 4) include the following, as applicable:

- Hematology: hemoglobin, platelets, international normalized ratio (INR), white blood cell count (WBC), lymphocytes (absolute; only for Cohort 1 participants > 13 years old), and neutrophils + bands (absolute; ANC);
- Hepatobiliary enzymes and measures of hepatic synthetic function: alanine aminotransferase (ALT), aspartate aminotransferase (AST), alkaline phosphatase, total bilirubin, and albumin;
- Pancreatic enzymes and renal function tests: lipase (colorimetric or turbidimetric) and creatinine;
- Electrolytes: bicarbonate (low), calcium (high and low), phosphate (low), potassium (high and low), and sodium (high and low).

See Protocol Appendix 5 for DAIDS toxicity grades.

In the absence of DAIDS toxicity grades, the following toxicity grade categories are provided for creatinine clearance using the Schwartz formula:

- SI units (mL/s/ m^2): < 0.25 (Grade 4); 0.25 to < 0.50 (Grade 3); 0.50 to < 1.0 (Grade 2); 1.0 to < 1.5 (Grade 1); \ge 1.5 (Grade 0);
- US units (mL/min/1.73 m²): < 15 (Grade 4); 15 to < 30 (Grade 3); 30 to < 60 (Grade 2); 60 to < 90 (Grade 1); ≥ 90 (Grade 0).

General Medical History

A by-participant listing of general medical history is provided for enrolled participants.

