6.6.4 Clinical Laboratory Evaluations

Summaries are based on treated participants with at least one laboratory measurement during the analysis period. All output is presented separately for SI and US units.

EOT toxicity grades and values are determined form the last laboratory test value collected during the on-treatment analysis period.

End of study (EOS) toxicity grades and values are determined form the last laboratory test value collected during the follow-up analysis period.

By-participant listings are provided for enrolled participants for the following laboratory tests:

- Hematology: hematocrit, hemoglobin, platelets, INR, WBC, lymphocytes (absolute), and ANC;
- Hepatobiliary enzymes and measures of hepatic synthetic function: ALT, AST, AST to platelet ratio index (APRI), alkaline phosphatase, total bilirubin, albumin, and alpha fetoprotein;
- Pancreatic enzymes and renal function tests: lipase (colorimetric or turbidimetric), creatinine, and creatinine clearance using the Schwartz formula;
- Electrolytes: bicarbonate, calcium, phosphate, potassium, and sodium.

These listings identify laboratory abnormalities using toxicity grades as specified in Section 6.3.2.4.

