6.6.4.3 Select Laboratory Test Results

Select laboratory test endpoints are summarized as categorical parameters as follows for treated participants, unless specified otherwise:

- Confirmed creatinine clearance $< 1.0 \text{ mL/s/m}^2 \ (< 60 \text{ mL/min/1.73m}^2)$ using the Schwartz formula on treatment. Confirmed is defined as ≥ 2 consecutive values meeting the criteria on treatment.
- ALT normalization (i.e., ALT \leq 1 x upper limit of normal [ULN]) at EOT by baseline ALT category (all; ALT \leq 1 x ULN; ALT > 1 x ULN; not reported) on treatment.
- ALT normalization at EOS by EOT ALT category (all; ALT \leq 1 x ULN; ALT > 1 x ULN; not reported) during follow-up for follow-up participants.
- AST normalization (i.e., AST \leq 1 x ULN) at EOT by baseline AST category (all; AST \leq 1 x ULN; AST > 1 x ULN; not reported) on treatment.
- AST normalization at EOS by EOT AST category (all; AST \leq 1 x ULN; AST > 1 x ULN; not reported) during follow-up for follow-up participants.
- Potential Drug Induced Liver Injury (PDILI) on treatment or during follow-up, defined as concurrent (1) ALT ≥ 5 x minimum(baseline, nadir), and ALT ≥ 10 x ULN, and (2) total bilirubin ≥ 2 x ULN. Concurrent is defined as the total bilirubin elevation occurring within 30 days after the ALT elevation.

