- Exclusion criterion 3c: Albumin < 35 g/L or < 3.5 g/dL
- Exclusion criterion 3d: Total bilirubin > 19 μmol/L or > 1.1 mg/dL without history of Gilbert syndrome. Gilbert syndrome is identified from general medical history specify details (#);
- Exclusion criterion 3e: Alpha fetoprotein > 50 ng/mL or > 50 µg/L
- Exclusion criterion 3f: ANC $< 1.5 \times 10^9$ cells/L or $< 1.5 \times 10^3$ cells/ μ L
- Exclusion criterion 3g: Hemoglobin < 100 g/L or < 10 g/dL
- Exclusion criterion 3h: Platelets < 100 x 10⁹ cells/L
- Exclusion criterion 3i: Creatinine clearance < 1 mL/s/m² or < 60 mL/min/1.73m², using the Schwartz formula.
- (#) Non-study medications and medical conditions marked above with # are identified by a BMS physician prior to database lock.

The screening portion of the pre-treatment analysis period begins at informed consent and ends before the start of study therapy (Day 1).

[figure not shown]
A participant with multiple pre-treatment measurements (e.g., HCV RNA) is considered to have an eligibility deviation only if all pre-treatment measurements meet the deviation criterion.

Participant Management Deviations

Participant management deviations are evaluated during the on-treatment or follow-up analysis period for the following categories:

- At least 2 consecutive missed doses of DCV before Day 10 PK sampling, or at least 1 missed dose of DCV within 2 days before Day 10 PK sampling. Missed doses of DCV are identified from interruptions or gaps between dosing records;
- At least twice of DCV target daily dose taken within 2 days before Day 10 PK sampling;
- DCV or SOF average daily dose < 80% of target daily dose;
- DCV or SOF interruption > 7 consecutive days;
- Continuation of study therapy after having virologic breakthrough;
- Use of prohibited non-study concomitant medication for more than 1 day, including anti-HCV medications (#). Generic drug names are presented alphabetically as subcategories;
- Use of non-study anti-HCV medication during follow-up (#). Generic drug names are presented alphabetically as subcategories;
- (#) Non-study medications marked above with # are identified by a BMS physician prior to database lock.

Anti-HCV Medications

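### Creatinine-clearance grading: the SAP's SI limits fit only mL/s/1.73 m², not the printed mL/s/m², and its custom scale is out of step with the DAIDS version now in Protocol Appendix 5

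*SAP*

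**What the plan says.** **Unit.** SAP 6.3.2.4 sets out two parallel grading scales for Schwartz creatinine clearance. The SI scale reads "SI units (mL/s/ m^2): < 0.25 (Grade 4); 0.25 to < 0.50 (Grade 3); 0.50 to < 1.0 (Grade 2", with Grade 1 from 1.0 and Grade 0 from 1.5. The US scale reads "US units (mL/min/1.73 m²): < 15 (Grade 4); 15 to < 30 (Grade 3); 30 to < 60 (Grade 2", with Grade 1 from 60 and Grade 0 from 90. The top pairing recurs in SAP Appendix 1, in the programmed check of exclusion 3i: "Creatinine clearance < 1 mL/s/m² or < 60 mL/min/1.73m², using the Schwartz formula". It recurs again in SAP 6.6.4.3, where the confirmed on-treatment flag treats 1.0 mL/s/m² and 60 mL/min/1.73 m² as the same limit. SAP 6.6.4 adds: "All output is presented separately for SI and US units".

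**Version.** SAP 6.3.2.4 cites the 2004 DAIDS table and justifies the custom scale on the ground that DAIDS offers no grades for this test. It then directs the reader to Protocol Appendix 5 for the DAIDS grades. That appendix now reproduces version 2.1 (July 2017), which has a row for low creatinine clearance or eGFR and names the Schwartz formula in its footnote. Protocol 10.3.3 likewise cites December 2004 (clarified August 2009) while linking to Appendix 5.

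**The concern.** The SI and US limits are meant to be the same cut-offs in two units. With the SI unit as printed they are not, so a programmer who followed the text literally could give one participant two different grades for one sample.

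The version problem does not depend on the unit. The current text leaves open whether low creatinine clearance is graded on the SAP's scale or on the table the SAP points to, and the two give different grades.

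Laboratory abnormalities by toxicity grade are part of a secondary safety endpoint (Protocol 4). The note in Protocol 10.3 keeps laboratory tests among the data to be reported after early termination. SAP 6.6.4 and 6.6.4.1 take their grades from 6.3.2.4, so the listings and the on-treatment and follow-up summaries inherit whatever that section says.

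**Working it through.** **1. Unit check.** The inputs are the four US limits and four SI limits in SAP 6.3.2.4. A value of x mL/min/1.73 m² equals x/60 mL/s/1.73 m², or x/60/1.73 mL/s/m². In reverse, s mL/s/m² equals s × 60 × 1.73 mL/min/1.73 m².

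| US limit | x/60 (per 1.73 m²) | x/60/1.73 (per m²) | SI limit printed | Printed limit × 60 × 1.73 |
|---|---|---|---|---|
| 15 | 0.25 | 0.145 | 0.25 | 25.95 |
| 30 | 0.50 | 0.289 | 0.50 | 51.9 |
| 60 | 1.0 | 0.578 | 1.0 | 103.8 |
| 90 | 1.5 | 0.867 | 1.5 | 155.7 |

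The printed SI numbers are reproduced exactly per 1.73 m². Per m², all four are off by the same factor, 1.73.

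**2. What follows for grades.** If the SI data are held per 1.73 m², the SI and US grades agree at every value. If the data were converted to per m², a value of 100 mL/min/1.73 m² would be 100/60/1.73 = 0.963 mL/s/m². That is SI Grade 2 but US Grade 0, and it would meet the 1.0 limit in 6.6.4.3 and Appendix 1 without meeting the limit of 60. For values of 60 and above, the SI grade would then be one higher from 60 to <90, two higher from 90 to <103.8, one higher from 103.8 to <155.7, and equal from 155.7 up.

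**3. Version check.** The inputs are the SAP US scale and the absolute bands in Protocol Appendix 5, both in mL/min/1.73 m².

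| Value | SAP grade | Appendix 5 grade, absolute band |
|---|---|---|
| < 15 | 4 | 4 |
| 15 to < 30 | 3 | 4 |
| 30 to < 60 | 2 | 3 |
| 60 to < 90 | 1 | 2 |
| 90 and above | 0 | none |

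Appendix 5 is one grade higher for every value from 15 to <90. The combined Grade 3 to 4 category starts below 30 in the SAP and below 60 in Appendix 5.

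Appendix 5 also grades the fall from baseline: 10 to <30% is Grade 2, 30 to <50% is Grade 3, and 50% or more is Grade 4. It applies whichever criterion gives the higher grade. The SAP has no such rule. For a fall from 130 to 100, (130 − 100)/130 = 23%, which is SAP Grade 0 but Appendix 5 Grade 2.

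**4. Which bands can be occupied.** Protocol exclusion 3i removes participants with "Creatinine clearance < 60 ml/min as calculated by the Schwartz formula". At baseline, therefore, the only band in practice where the SAP and Appendix 5 differ is 60 to <90. Lower bands and the percent-fall criterion matter after baseline.

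**The case against.** The strongest reply on the unit is that this is a label slip with no shown effect. That largely stands. The protocol gives the formula only as "CrCl (ml/min/1.73m^2) = [length (cm) \times k] / Serum Cr", all four SI constants are the US limits divided by 60, and no section describes normalising to 1 m². Protocol exclusion 3i itself prints its limit without the 1.73 that its own formula carries, so the term is easily dropped. What does not stand is treating it as a one-off misprint: the same wrong pairing is in three separate SAP sections, each time beside a US unit that keeps its 1.73.

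A reader might infer that participants will receive conflicting SI and US grades, or that eligibility was misjudged. The documents support neither. The first needs a conversion to per m² that is nowhere described. As for the second, the protocol criterion uses 60 with a formula in mL/min/1.73 m², and the Appendix 1 check is only a retrospective deviation flag, raised "only if all pre-treatment measurements meet the deviation criterion".

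On the version, the reply is that the SAP still describes the full 30-participant design and simply was not updated when Revised Protocol 01 replaced Appendix 5. That is probably how it arose. A reader might go further and infer that the SAP was wrong to say DAIDS had no grades for this test. The 2004 table is not in the documents, so that cannot be said. The conflict between current texts remains all the same.

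A reader might also cite the rule in SAP 7.4.4 that puts an ALT of 2.53 × ULN in Grade 2. It is no evidence of a mismatch, because Appendix 5 gives Grade 2 as well.

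Finally, Protocol 10.3 keeps only select safety assessments and rules out statistical analyses. How much of the graded output, the 6.6.4.3 flag or the deviation summary will appear is therefore uncertain.

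**Conclusion.** There are two separate, minor errors.

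- **Unit.** The printed SI unit does not match the US limits; this is certain from the arithmetic. That anyone is actually misgraded is unlikely, because it requires SI data held per m². If the data are per 1.73 m², no grade changes.
- **Version.** This is the more consequential of the two. Whatever the SI unit, the SAP scale and the table it refers to grade creatinine clearance differently from 15 to <90, and differently again for falls from baseline. The documents do not settle which governs.

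The effect is confined to descriptive laboratory grades and flags in 5 participants, to the extent that these are still reported. With so few, one changed grade moves a summary by one in five. The listings show the creatinine-clearance values themselves, so a reader can check a grade against its value. Eligibility, PK and SVR12 are unaffected.

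**What to change.** **Unit.** In SAP 6.3.2.4, 6.6.4.3 and Appendix 1 (exclusion 3i), relabel the SI unit mL/s/1.73 m² and confirm that the SI data are held in that unit. Alternatively, grade once in mL/min/1.73 m² and carry that grade to both displays. The cost of relabelling is three label corrections and one data check.

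**Version.** State one governing DAIDS version consistently in SAP 6.3.2.4, Protocol 10.3.3 and Appendix 5.

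- If version 2.1 governs, replace the custom scale with the Appendix 5 creatinine-clearance grades and check the other graded tests. One of these is the lymphocyte age limit: the SAP grades only Cohort 1 participants over 13 years, Appendix 5 those over 5 years. In a cohort aged 12 to <18 this matters only for anyone not over 13. The cost is programming the percent-fall criterion and the higher-grade rule, plus that check.
- If the 2004 table governs, remove the pointer to Appendix 5 for laboratory grades and say that the custom scale is kept. The cost is wording only.

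Neither route needs new data.

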6.3.2.5 Prior Non-Study Medications

Prior non-study medications are summarized as categorical parameters alphabetically by anatomic class, therapeutic class, and generic name. Prior non-study medications are defined as those taken before the start of study therapy. These are previous non-study medications (i.e., those taken before informed consent) or current non-study medications (i.e., those taken on or after informed consent to before the start of study therapy).

6.4 Extent of Exposure

Extent of exposure is summarized for treated participants, unless specified otherwise. See Section 7.3 for derived dates and Section 7.4.2 for additional conventions.

6.4.1 Study Therapy and Follow-up

The following time-to-exposure-events (weeks) are summarized as continuous parameters:

- Time on study therapy. Defined as (study therapy end date study therapy start date + 1)/7.
- Time on each study drug and formulation: DCV (any formulation); DCV tablet; DCV chewable tablet; SOF (any formulation); SOF tablet; SOF pediatric formulation to be determined (TBD). Defined analogously to time on study therapy based on individual start/end dates derived for each drug and formulation.
- Time in follow-up for follow-up participants. Defined as (last contact date study therapy end date + 1)/7.
- Time on study. Defined as (last contact date study therapy start date + 1)/7.

6.4.2 Interruption of Study Therapy

Participants with dose interruptions of > 3 consecutive days (including reasons for dose modification) are summarized as categorical parameters for each drug (DCV and SOF).

6.4.3 Concomitant and Post-Treatment Non-Study Medications

Concomitant medications are summarized as categorical parameters alphabetically by anatomic class, therapeutic class and generic name for treated participants. These are non-study medications taken on or after the start date of study therapy and through the last date of study therapy.

Post-treatment medications are summarized analogously for follow-up participants. These are non-study medications taken any time after the last date of study therapy.

A by-participant listing of all non-study medications (i.e., previous, current, concomitant, post-treatment) is provided for enrolled participants.

6.5 Efficacy

All efficacy endpoints in this study are either secondary and are assessed for treated participants unless specified otherwise.

Analyses use HCV RNA results from the central laboratory only. Visit windows are constructed around planned visit times for slotting purposes.

For all efficacy analyses, HCV RNA measurements are excluded after the start date of non-study anti-HCV medication on treatment or during follow-up (see Section 7.3).

A by-participant listing of HCV RNA values (in both IU/mL and log₁₀ IU/mL) is provided for enrolled participants. Values meeting the criteria for virologic breakthrough and relapse at any visit are flagged (see Section 6.5.1.2).

The end of treatment (EOT) HCV RNA value is determined from the last HCV RNA value collected during the on-treatment analysis period.

See also Section 7.4.7 for virology conventions.

6.5.1 Primary and Secondary Efficacy Endpoints

6.5.1.1 SVR12

The proportion of treated participants with SVR12, defined as HCV RNA < LLOQ TD or TND at follow-up Week 12, are presented with 2-sided 95% CIs using the following 3 methods:

- Next Value Carried Backwards (NVCB): The numerator is based on participants meeting the response criteria, and the denominator is based on all treated participants. Participants with missing HCV RNA data at follow-up Week 12 have data imputed using the next and closest available HCV RNA measurement after the follow-up Week 12 HCV RNA visit window.
- Modified (mITT): The numerator is based on participants meeting the response criteria, and the denominator is based on all treated participants. Participants with missing follow-up Week 12 HCV RNA are counted as non-responders (i.e., missing data are not imputed).
- Observed values: The numerator is based on participants meeting the response criteria, and the denominator is based on treated participants with an evaluable HCV RNA measurement at follow-up Week 12 (i.e., participants with missing data are excluded).

NVCB is the principal analysis method, whereas mITT and observed values are sensitivity analysis methods.

SVR12 treatment outcomes are summarized using NVCB in the following categories:

- Responder
- Non-responder
 - o Non-responder with HCV RNA < LLOQ TND at EOT
 - Relapser. Defined as HCV RNA < LLOQ TND at EOT and HCV RNA ≥ LLOQ at follow-up Week 12

 - Other non-responder. Defined as HCV RNA < LLOQ TND at EOT and missing HCV RNA at follow-up Week 12 and thereafter.

Percentages for relapse and other non-responders are calculated based on treated participants with HCV RNA < LLOQ TND at EOT.

- On-treatment failure
 - Virologic breakthrough. Defined as either (1) confirmed ≥ 1 log₁₀ IU/mL HCV RNA increase from nadir on treatment, or (2) confirmed HCV RNA ≥ LLOQ on treatment after HCV RNA < LLOQ TD or TND on treatment. Confirmed is defined as ≥ 2 consecutive measurements.

 - Other on-treatment failure
- o No post-baseline HCV RNA value

6.5.1.2 Virologic Resistance

Resistance testing is performed post-baseline for participants with HCV RNA ≥ 1,000 IU/mL who have experienced virologic failure, defined as any of the following:

- Virologic breakthrough at any on-treatment visit (see Section 6.5.1.1);
- Relapse at any follow-up visit (see Section 6.5.1.1);
- Other: HCV RNA ≥ LLOQ at any visit not meeting the definition of virologic breakthrough or relapse.

Virologic resistance is assessed for SVR non-responders with paired genotypable isolates, i.e., genotypable at baseline and at least one post-baseline visit. SVR non-responders are those who did not achieve SVR using observed values at a follow-up visit through follow-up Week 108 (see Section 6.5.1.1). The following are summarized as categorical parameters at key amino acid positions defined in APPENDIX 2:

- Emergent NS5A and NS5B genotypic substitutions. An emergent substitution is a post-baseline substitution that was not detected at baseline;
- Replacements of NS5A and NS5B emergent genotypic substitutions. A replacement of an
 emergent substitution occurs when only the reference or baseline sequence is detected at the
 last post-baseline genotypable isolate.

A by-participant listing of all NS5A and NS5B genotypic substitutions is provided for enrolled participants. This listing identifies key NS5A and NS5B key substitutions, as well as emergence and replacement of these key substitutions.

6.6 Safety

Safety endpoints include the frequencies of AEs, SAEs, AEs leading to discontinuation of study therapy, deaths and other significant AEs as reported on CRFs. Other safety endpoints include the frequencies of laboratory abnormalities, and changes from baseline in safety parameters (i.e., laboratory tests, ECGs, vital signs, and physical measurements) over time.

Safety endpoints are summarized separately for (1) treated participants during the on-treatment analysis period, and (2) follow-up participants during the follow-up analysis period, unless specified otherwise.

Analyses of safety data are cumulative through the time of database lock.

6.6.1 Deaths

Deaths are identified from two sources of information:

- Subject status CRF: Study discontinuation reason of death;
- AE/SAE CRF: Any of the following parameters: SAE outcome of death; SAE category of death; non-missing character death date.

A by-participant listing of death is provided for enrolled participants, which includes the death date, time to death (weeks), source of information, and cause of death.

Time to death (weeks) is defined as (death date - start date of study therapy + 1)/7.

